Focus group format: Up to 16 adult (\geq age 18) family members of individuals with CPD will be invited to participate in 2 focus groups conducted by [name] and trainees at the Tanzania site. Family members will all have regular contact with patients (contact a minimum of 3 days/week). Family member focus groups will comprise 6-10 individuals each, and will last up to approximately 90 minutes. Focus groups will be audio-recorded and transcribed verbatim and supplemented with the addition of copious field-notes. Up to 16 health workers will be invited to participate in 2 additional focus groups, using similar format as the family focus groups. Health workers (nurses, doctors, social workers, pharmacists) will be recruited from clinic and hospital-based settings and have experience interacting with patients with CPD. *Individual interview format:* Up to 15 patients with CPD will be interviewed regarding barriers and facilitators to medication adherence. Data recording will be the same as with focus groups.

Phase 2

In Phase 2/Aim 2, informed by the mixed-methods data from Phase 1, the study team will adapt the CAE-L intervention to be culturally and linguistically appropriate for the Tanzanian setting. The “deliverable” of Phase 2 will include a manualized intervention that combines a psychosocial intervention to promote adherence + use of LAI.

Phase 3

In Phase 3/Aim 3, the study team will select appropriate measures, train staff in measure implementation, and finalize CAE-L for delivery. Social worker interventionists will be trained to deliver CAE-L. Finally, the study will roll-out and evaluate CAE-L in 20 individuals with CPD in a 6-month (25-week) prospective training/proof-of-concept exercise. CAE-L will be further refined based upon input from interventionists and study participants. The “deliverable” of Phase 3 will include building capacity of a clinical trials infrastructure that includes identification of relevant tools/ measures and appropriately trained staff who are capable and available to conduct research to improve health outcomes for people with CPD in Tanzania.

Phase 3 Study Population:

The study will enroll 20 adult patients with the following criteria:

Inclusion Criteria:

1. Individuals age 18 and older with schizophrenia or schizoaffective disorder.

2. Known to have medication treatment adherence problems as identified by the TRQ (20% or more missed medications in past week or past month)

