3. Ability to be rated on psychiatric rating scales.
4. Willingness to take long-acting injectable medication
5. Able to provide written, informed consent to study participation.

Exclusion Criteria:

1. History of allergy or intolerance to haloperidol or haloperidol decanoate.
2. Individuals on long-acting injectable antipsychotic medication immediately prior to study enrollment.
3. Medical condition or illness, which in the opinion of the research psychiatrist, would interfere with the patient's ability to participate in the trial.
4. Physical dependence on substances (alcohol or illicit drugs) likely to lead to withdrawal reaction during the course of the study in the clinical opinion of the treated research psychiatrist.
5. Immediate risk of harm to self or others.
6. Female who is currently pregnant or breastfeeding.

A Screening Form for each patient will be completed regardless of whether the patient is ultimately enrolled. The form will detail reasons for exclusion, allowing an estimate of sample generalizability. All study procedures will be conducted at Muhimbili Hospital and its associated ambulatory clinics.

LAI: Patients on oral haloperidol will be switched to haloperidol decanoate as per manufacturer's package insert. Individuals not on antipsychotic medication at the time of screening assessment or who are on a different antipsychotic medication, will receive an oral tolerance test (OTT) consisting of up to 14 days of oral haloperidol 2-5 mg twice daily. If the OTT suggests good tolerability, the participant will then receive LAI (haloperidol decanoate) intramuscularly after completion of baseline assessments. Dosing of LAI will be as clinically indicated using conservative dosing to minimize drug-related adverse effects. In the CWRU studies, mean end-point dose of haloperidol decanoate was 68.0 mg, SD 21.1, Range 50-100 mg/monthly injection. It is anticipated that patients will continue on the same dose for 6 months, although dose changes will be permitted based upon clinical status. Each study participant will receive up to 8 injections during the study.

Concomitant treatments: Stable dose psychotropic drugs (> 30 days of previous use) other than antipsychotics will be continued. New psychotropic medications will be strongly discouraged. Medications for side effects may be given at the discretion of the treating psychiatrist and their use will be recorded.

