Baseline information will include previous illness history including duration of psychiatric illness, past hospitalizations, suicide attempts, medication treatment history and cumulative medical burden as evaluated by the self-reported Charlson Index. Table 1 illustrates Phase 3 schedule of procedures. Primary outcomes will be change on TRQ and mean LAI injection frequency. Secondary outcomes will include additional information on adherence attitudes (DAI), CPD symptoms (BPRS, CGI), and Social functioning (SOFAS). The Alcohol, Smoking and Substance Involvement Screening Test (ASSIST) and Alcohol Use Disorders Identification Test (AUDIT) (53) will assess substance use. All outcome assessments will be conducted at study baseline, Week 13, and at Week 25 follow-up.

Primary Outcome:

Treatment adherence behavior will be evaluated with the self-reported Tablets Routine Questionnaire (TRQ) and adherence with regular LAI injections. The literature on measurement of treatment adherence, including the PI's work in this area ([name] 2004, [name] in Press-a, Colom 2005) recommends multiple-method assessments to fully characterize treatment adherence. A total combined adherence score (proportion of medications taken out of total medications prescribed) will be calculated as an average of the TRQ values of all orally-prescribed medications. LAI injection frequency will also be assessed.

The Tablets Routine Questionnaire: (TRQ) (Scott 2002, Peet 1991) has been noted by other investigators to be reliable and appropriate for use in seriously mentally ill populations (Peet 1991, Scott 2002). The TRQ determines proportion of prescribed medication taken and is not dependent upon timing of medication provided that medication is consumed within the required day/24 hour period. This rating has demonstrated statistically significant association with past non-adherence, repeated past non-adherence, any non-adherence in the past month, and non-adherence in the past week ($X^2=7.2$, $df=6$, $p=.03$). Compared with non-adherence in the past two years, missing 30% or more of prescribed mood stabilizers in the past week has a specificity of 100% and a sensitivity of 65%. Compared with non-adherence in the past week, it has specificity of 87% and a sensitivity of 84% (Scott 2002). The TRQ format will be modified slightly to document all adherence values (an exact proportion) for each item.

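### Change on TRQ, a primary outcome, averages all oral drugs while the antipsychotic moves to injection, so baseline and follow-up scores generally cover different drugs, or none at follow-up

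*Combined protocol and SAP*

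**What the plan says.** The statistical plan is the closing section of the protocol. Phase 3 Study Measures states: "Primary outcomes will be change on TRQ and mean LAI injection frequency". Under Primary Outcome, a combined adherence score is "calculated as an average of the TRQ values of all orally-prescribed medications", and injections are assessed separately. The protocol does not say outright that change on TRQ means change in this combined score, but it is the only score defined and the natural reading.

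The LAI paragraph then changes what is taken by mouth:

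- "Patients on oral haloperidol will be switched to haloperidol decanoate".
- Participants on no antipsychotic, or on a different one, "will receive an oral tolerance test (OTT) consisting of up to 14 days of oral haloperidol". If they tolerate it, they receive the injection once baseline assessments are done.

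Concomitant treatments adds "Stable dose psychotropic drugs (> 30 days of previous use) other than antipsychotics will be continued" and "Medications for side effects may be given at the discretion of the treating psychiatrist and their use will be recorded".

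On timing, the text places outcome assessments at baseline, Week 13 and Week 25. Table 1 marks TRQ at every visit from Screen to V8, and its footnote lets Screen and V1 be combined. The Phase 3 paragraph of Statistical Analysis promises descriptive summaries and a pre-post comparison. It has no rule for a participant with no oral drug.

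**The concern.** A pre-post change is informative when the same quantity is measured twice. Here the treatment itself takes a drug out of the average, and that drug is the one whose adherence the project targets: the Purpose overview defines high risk by missed antipsychotic medication. Side-effect drugs may also join the average after baseline.

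Two things follow if the rule is applied as written. The mean TRQ change can move because the list of drugs changed, not because anyone took medication differently. And an analyst facing a participant with no oral drug at Week 13 or Week 25 has to improvise a score, in a study of 20 where a few such choices can set the result.

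**Working it through.** **No figure to reproduce.** The documents give no power calculation, standard deviation or expected TRQ change for Phase 3. The sample size of 20 is from Phase 3 Study Population. All adherence levels and drug counts below are assumptions, except that 0.80 is the entry threshold (20% missed).

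**Step 1: which drugs are averaged.** Take a participant who enters on one oral antipsychotic and k other oral drugs.

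| Time | Oral drugs in the average |
|---|---|
| Baseline | antipsychotic + k others |
| Weeks 13 and 25, after the switch | k others, plus any oral side-effect drug added |

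**Step 2: shift with unchanged behaviour.** Let a be the proportion of the antipsychotic taken and b that of each other drug, both constant, with no drug added.

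- Baseline = (a + k·b)/(k + 1)
- Follow-up = b
- Shift = b − (a + k·b)/(k + 1) = (b − a)/(k + 1)

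Example: a = 0.50, b = 0.90, k = 1. Baseline = (0.50 + 0.90)/2 = 0.70, follow-up = 0.90, shift = +20 points. Using only the drug common to both times gives 0.90 and 0.90, a change of 0.

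Shift in percentage points:

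| a | b | k = 1 | k = 2 | k = 3 |
|---|---|---|---|---|
| 0.50 | 0.50 | 0 | 0 | 0 |
| 0.50 | 0.90 | +20 | +13.3 | +10 |
| 0.80 | 0.50 | −15 | −10 | −7.5 |
| 0.80 | 0.90 | +5 | +3.3 | +2.5 |

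Both signs occur.

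**Step 3: no oral drug left.** With k = 0 and nothing added, the follow-up average has no denominator. Suppose half of the 20 are in this position, everyone has a baseline of 65%, and the rest do not change. The mean change is then:

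- 0 if they are left out;
- 0.5 × (100 − 65) = +17.5 points if they are scored 100%;
- 0.5 × (0 − 65) = −32.5 points if they are scored 0%.

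**Step 4: which baseline.** TRQ is taken at Screen and at V1, and a tolerance test of up to 14 days can fall between them. If V1 directly follows a full 14-day test, a past-week TRQ lies wholly inside the test (7 of 7 days). A past-month TRQ (30 days assumed) has up to 14/30 = 47% of its days inside it. The plan does not say which TRQ is the baseline, or whether tolerance-test haloperidol counts.

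**The case against.** - **The rule already says which drugs count.** A reader might infer that the plan is silent on this. It is not: read literally, all oral drugs count. The gap is that the set is not held constant between visits and the empty set has no rule.
- **The plan never says that every oral antipsychotic stops.** This stands. The switch follows a package insert that is not reproduced, so any oral overlap is unknown. Oral dispensing is marked at Screen only in Table 1, but that is weak evidence, because continued psychotropics have no later dispensing mark either. Injection after baseline is written for the tolerance-test group; for those already on oral haloperidol the timing comes from Table 1 alone. Hence the word generally. Overlap would remove the problem only if it lasted to the follow-up visit being compared.
- **On-study antipsychotic adherence has its own primary measure.** This stands: the plan uses injection adherence beside TRQ. It limits what rests on TRQ but does not make the TRQ change comparable over time.
- **Phase 3 has 20 participants and deliberately limited quantitative analysis.** This stands and caps the consequence. The plan nevertheless names TRQ change as primary and promises the pre-post comparison.
- **Values per drug would let an analyst separate the shift out.** This is true if values are stored by drug. The plan records an exact proportion for each item, without saying that an item is a drug.

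**Conclusion.** The concern holds. For participants who enter on an oral antipsychotic, the stated average generally compares different drug sets before and after, and it gives no score where no oral drug remains. With behaviour unchanged the change score moves by (b − a)/(k + 1), or +20 points in the worked example. Size and sign depend on adherence levels and drug counts that the documents do not give.

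Three stronger readings are not supported:

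- **That the entry rule guarantees a spurious rise.** Entry requires: "Known to have medication treatment adherence problems as identified by the TRQ (20% or more missed medications in past week or past month". With b = 0.90 and k = 1, this would imply at least (0.90 − 0.80)/2 = +5 points if the 20% applies to the antipsychotic. If it applies to the combined score, a ≤ 0.70 and the rise is at least (0.90 − 0.70)/2 = +10. Either holds only if the baseline is the same TRQ and recall window used for entry. With V1 as baseline and full adherence during the tolerance test (a = 1.0, b = 0.90, k = 1), the score goes from 95% to 90%, a fall of 5 points.
- **That all participants lose their TRQ score.** Stable non-antipsychotic psychotropics continue, and the share with no oral drug is not given.
- **That the study will reach a wrong decision.** Phase 3 is descriptive and has no test threshold. The consequence is a TRQ change that is hard to interpret.

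**What to change.** Add a scoring rule before analysis:

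1. Report TRQ separately for oral antipsychotics and for other oral drugs. Base any pre-post TRQ change on the same drugs at baseline and at the follow-up visit, not on the all-drug average. Describe drugs started or stopped after baseline separately.
2. At Week 13 and Week 25, report the number evaluable and the number with no common oral drug. Leave the latter out of the change score; do not score them 0% or 100%.
3. Report the entry oral-antipsychotic TRQ as a baseline characteristic beside on-study injection adherence, without calling the difference a change score. One is self-report and the other counts injections. Injection adherence also has no value immediately before the study, because the exclusion criteria remove "Individuals on long-acting injectable antipsychotic medication immediately prior to study enrollment".
4. Name the baseline TRQ (Screen or V1) and its recall window, and state whether tolerance-test haloperidol counts in it.

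**Cost.** This is an analysis rule, and it needs no new assessments provided TRQ values are stored by drug. Whether it must be submitted is for the two review boards. The downsides should be stated with the results:

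- Fewer participants contribute. If 25%, 50% or 75% have a common oral drug (assumed, before attrition), that is 5, 10 or 15 of 20. With an assumed SD of change of 30 points, the 95% half-width t(0.975, n − 1) × 30/√n is 37.2, 21.5 or 16.6 points, against 14.0 with all 20.
- The change score mainly describes non-antipsychotic drugs.
- Requiring a drug at both visits conditions on persistence. A drug stopped because it was not being taken leaves the comparison, which can hide poor adherence. This is why item 1 asks for stopped drugs to be described.

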LAI Injection Adherence: LAI injection adherence will be determined as a proportion of LAI (paliperidone palmitate or haloperidol decanoate) injections received at the appropriate time (within 7 days of scheduled time).

Secondary Outcome:

Adherence Attitudes: The Drug Attitude Inventory (DAI), is used to measure attitudes towards medication among individuals with serious mental illness (Awad 1993), and is known to be relatively unaffected by psychiatric symptom severity ([name] 2002). The DAI was originally developed to assess the attitudes and subjective experience of patients with schizophrenia being treated with antipsychotic medications and has also been widely utilized with other seriously mentally ill populations receiving psychotropic medication ([name] 2003). The 10-item version of the scale will be utilized (Awad 1993). The DAI is a simple, true-false format questionnaire that assesses domains of patient's attitudes including positive and negative experience, locus of control, and attitudes towards health. Responses are scored on a euphoric-dysphoric continuum ($\alpha= 0.93$).

Symptoms: Symptoms of schizophrenia and schizoaffective disorder will be addressed using the Brief Psychiatric Rating Scale (BPRS) developed by Overall and colleagues (1962).

The BPRS, developed by Overall and Gorham (1962), is a widely used, relatively brief scale that measures major psychotic and non-psychotic symptoms in individuals with SMI. The 18-item BPRS is

well-validated and is perhaps the most researched instrument in psychiatry. Reliability coefficients are reported to be in the range of 0.56-0.87.

Global psychopathology: Global psychopathology will be measured with the Clinical Global Impressions (CGI) (Guy, 1976) a widely used scale which evaluates illness severity on a 1 to 7 point continuum. Severity of illness ratings on the CGI have reported reliability scores ranging from 0.41-0.66 (Guy, 1976).

Social Functioning: Life and Work Functional status will be evaluated using the Social and Occupational Functioning Scale (SOFAS), which is derived from the GAF. The GAF is a 100-point single-item scale which measures global functioning of psychiatric patients and is widely utilized in clinical studies involving Seriously Mentally Ill patients (Jones, 1995). The reliability of the GAF ranges from 0.62-0.82.

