If a woman becomes pregnant while in the study, the PI will make a clinical decision as to whether the study drug will be discontinued based on the risk/benefit ratio for use of that specific drug in pregnant women. As with all subjects who discontinue medication early but wish to continue in the study, these women will be permitted to complete the CAE sessions and the remaining study visits.

Major psychiatric illness

Because this is a study evaluating the effectiveness of CAE and long-acting injectable antipsychotic medication on people with schizophrenia or schizoaffective disorder, subjects must have been diagnosed

with one of these major psychiatric illnesses to be able to participate. The capacity to which an individual within this subpopulation is able to give consent may vary from individual to individual. To acknowledge this issue, procedures have been put in place to ensure that each individual is capable of giving signed written consent. A witness who is not part of the study team will sign the consent form to ensure that the study was thoroughly explained to the participant and that they comprehend the study procedures and the associated risks and benefits of participating. Within this subpopulation are also individuals who may have a Legally Authorized Representative (LAR). For these individuals, the signed written consent of the LAR is required in addition to the individual's signed written consent. If an individual is deemed unable to provide signed written consent, they will not be permitted to participate, regardless of the presence of signed written consent from the LAR.

Illiterate individuals

Some participants may be unable to read. In that case the ICF will be read to them in the presence of a witness who will co-sign the consent form.

Non-English speaking individuals

Participants will be residents of Tanzania. All study documents presented to the participants (ICF, surveys, flyers, if applicable) will be translated to Swahili; the research personnel at the study site will be fluent in the local language.

Plan for Obtaining Informed Consent:

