Component 2: [name] & [name] will co-lead regular research staff meetings to closely monitor study start-up and progress, including oversight of staff training and research capacity building. These meetings (held via SKYPE conference will be held approximately every other week for the first 3 months of the project and then at least once a month by web teleconference thereafter. Meeting minutes will be sent to all research staff participants. Regularly scheduled conference calls will be supplemented by more frequent local meetings and ad-hoc meetings that may be called in the event that problems or concerns arise. In addition, there will be 1-2 in-person visits to the sites annually. Any adverse or unexpected events will be reported in accordance with local IRB requirements.

Statistical Analysis:

Phase 1: First, the qualitative team will first independently review each transcript and highlight significant statements, sentences, or quotes. Based on review of the independently derived statements, the team will develop consensus-based “clusters of meaning” (58) or relevant “themes and categories” (58). Researchers will further read/code each document independently and iteratively until no new insights emerge.

These entries will be elaborated as coding progresses. The qualitative researchers will then construct a consensus-based coding dictionary that includes mutually exclusive definitions for each code. This coding structure will be reviewed after a preliminary analysis of a sub sample of transcripts, and the dictionary will be refined through comparison, categorization, and discussion (59-60). Then, using data and codes, the qualitative team will create code-based files across all

respondents. The team will further elaborate, refine, and differentiate the codes and identify similarities and differences through comparison of respondents.

Phase 3: Quantitative analysis will be limited as the focus is on feasibility, patient acceptability and research capacity-building. However, we will assess descriptive statistics and change from baseline in the primary and secondary measures using standard pre-post techniques.

References:

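### Change from baseline is planned for all primary measures, but LAI adherence has no informative baseline and no rule for scoring injections due after early stopping

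*Combined protocol and SAP*

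**What the plan says.** All references are to the combined protocol and SAP.

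- Study Measures, repeated in Phase 3 Study Measures: "Primary outcomes will be change on TRQ and mean LAI injection frequency". The same paragraphs add: "All outcome assessments will be conducted at study baseline, Week 13, and at Week 25 follow-up".
- LAI Injection Adherence defines the measure as "a proportion of LAI (paliperidone palmitate or haloperidol decanoate) injections received at the appropriate time (within 7 days of scheduled time".
- Statistical Analysis, Phase 3, calls the quantitative analysis limited because the focus is feasibility, acceptability and capacity-building, then states: "we will assess descriptive statistics and change from baseline in the primary and secondary measures using standard pre-post techniques".
- Exclusion criterion 2 removes: "Individuals on long-acting injectable antipsychotic medication immediately prior to study enrollment".
- The LAI paragraph says of those who pass the oral tolerance test: "the participant will then receive LAI (haloperidol decanoate) intramuscularly after completion of baseline assessments". It also says: "Each study participant will receive up to 8 injections during the study".
- Vulnerable populations, Pregnant Women, foresees people who stop the drug but remain in follow-up: "As with all subjects who discontinue medication early but wish to continue in the study". The Phase 3 risk text says that those who fail the tolerance test get no LAI.
- Table 1 marks LAI injection frequency at V1/Baseline, Week 13 and Week 25. It marks injections at V1, Week 1 (with a footnote making this one conditional on dosage), and Weeks 5, 9, 13, 17, 21 and 25.

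**The concern.** A pre-post analysis needs a baseline that could have taken more than one value. Here the eligibility rule fixes it. An analyst who follows the analysis text, the assessment-times sentence and Table 1 would calculate a change in LAI injection frequency and might report it as improved adherence. It would only show that an injectable was started in people who were not on one.

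The follow-up value has a related gap. The protocol expects some people to stop medication and stay in the study, yet gives no rule for scoring their remaining injections. If the count ends at the stop, someone who leaves treatment early can score 100%. Without a rule set in advance, the choice would be made after the injection data are seen.

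**Working it through.** **1. The plan's own count.** V1 (1) + conditional Week 1 (1) + Weeks 5, 9, 13, 17, 21 and 25 (6) = 8. This agrees with the stated maximum of 8, or 7 if the Week 1 injection is not given. Six injections after the first are scheduled for everyone.

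**2. The baseline value.** Under exclusion criterion 2:
- as a frequency, baseline = 0 for every participant by design;
- as an on-time proportion, baseline = 0 received / 0 scheduled, which is undefined.

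Earlier LAI use is not excluded, but no look-back measure of LAI adherence is described. With baseline 0 for all, change = p − 0 = p, where p is the follow-up proportion. It cannot be negative, and it repeats the follow-up level.

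**3. What a pre-post test would then show.** Assume 5 of 20 people stop after two of the six later injections and the other 15 have 6/6.
- Mean p = (15 + 5 × 2/6)/20 = 0.833; SD = 0.296.
- Standard error = 0.296/√20 = 0.0662.
- t = 0.833/0.0662 = 12.6 on 19 df.

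The test is overwhelmingly positive although a quarter of the group left treatment early.

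**4. The scoring of early stopping.** One person who stops after two on-time injections scores 2/2 = 100% if the denominator ends at the stop, or 2/6 = 33.3% if it stays at six.

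For n = 20, with k people stopping after s of six and all others at 6/6 (all assumed):
- denominator ending at the stop: mean = 100%;
- fixed denominator: mean = 1 − (k/20)(1 − s/6);
- gap = (k/20)(1 − s/6).

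| k | s | Fixed mean | Gap (points) |
|---|---|---|---|
| 1 | 4 | 98.3% | 1.7 |
| 1 | 2 | 96.7% | 3.3 |
| 3 | 4 | 95.0% | 5.0 |
| 3 | 2 | 90.0% | 10.0 |
| 3 | 1 | 87.5% | 12.5 |
| 5 | 4 | 91.7% | 8.3 |
| 5 | 2 | 83.3% | 16.7 |
| 5 | 1 | 79.2% | 20.8 |

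**5. Against sampling error.** The 95% half-width is t(19) × SD/√20, with t(19) = 2.093.
- k = 3, s = 2: SD 0.244, half-width 11.4 points, so the 10.0-point gap is smaller. The t interval is 78.6% to 101.4%, which passes 100%; a percentile bootstrap gives 80.0% to 100.0%.
- k = 5, s = 2: half-width 13.9 points, so the 16.7-point gap is larger.

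**6. Which early injections count.** With k = 5 and s = 2, adding V1 gives (15 + 5 × 3/7)/20 = 85.7%, up 2.4 points. Adding V1 and a given Week 1 injection gives (15 + 5 × 4/8)/20 = 87.5%, up 4.2 points. In this example the choice matters much less than the rule for stopping.

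**The case against.** The outcome sentence pairs change with the TRQ and a mean with LAI frequency. A specific outcome definition would ordinarily govern a general analysis sentence, and that sentence also provides for descriptive statistics. On this view LAI adherence is a descriptive follow-up measure and the V1 mark is harmless. This reading is available and probably intended. However, three places do not carry it through: the analysis sentence has no exception, the assessment-times sentence covers all outcomes, and Table 1 marks a baseline value.

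On the denominator, a reader might infer that the plan has none at all. That goes too far. Judging injections against a scheduled time presupposes a schedule, Table 1 supplies one, and the TRQ score is set against everything prescribed. A scheduled denominator is the ordinary reading. What is missing is narrower: whether the schedule continues to count after a stop, whether the conditional Week 1 injection counts, and how people who never start are handled.

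A fixed denominator is itself debatable. It counts a clinician-directed stop, such as one in pregnancy, as injections not received, and so mixes adherence with persistence. That objection stands, which is why such stops should be shown separately. Other fixed rules are defensible if stated in advance.

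**Conclusion.** The concern holds in a limited form and is minor. Followed literally, the plan asks for a pre-post change on a measure whose baseline is fixed at zero or undefined, and that change says nothing about adherence. The missing rule for early stopping could move the reported mean by 1.7 to 20.8 points. That range is illustrative: it assumes 1 to 5 of 20 people stopping after 1 to 4 of six injections, with perfect scores for all others. The documents give no expected discontinuation rate.

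A reader might infer that the primary analysis cannot be done, or that the sign of the result depends on the choice of baseline because V1 could be scored 1/1 and make change non-positive. The documents do not support either. A descriptive analysis is possible as the outcome is worded, and nothing in the text proposes the V1 injection as a baseline score. Severity is also held down by the setting: 20 people in one group, a feasibility focus, and no success threshold or power calculation tied to this outcome.

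**What to change.** 1. **Statistical Analysis, Phase 3:** limit change from baseline to the TRQ and the secondary measures. Report LAI adherence descriptively at Weeks 13 and 25, as a mean with a 95% CI that stays within 0 to 100% (for example, a percentile bootstrap).
2. **Table 1:** remove the V1 mark from the LAI injection frequency row.
3. **Study Measures and Phase 3 Study Measures:** exempt LAI adherence from baseline assessment in the sentence on assessment times. Otherwise step 2 creates a new conflict.
4. **Both measures sections and LAI Injection Adherence:** use one name and one definition, namely on-time injections out of those scheduled after the first. A workable form is the six at Weeks 5 to 25 (three by Week 13), leaving out the conditional Week 1 injection so that the denominator is the same for everyone. Keep the denominator fixed after discontinuation.
5. **Show separately** the clinician-directed stops and, out of all enrolled, those who never received a first injection.
6. **Reconcile** the LAI paragraph, which names haloperidol decanoate, with LAI Injection Adherence, which also names paliperidone palmitate. This changes no calculation here.

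The cost is wording and one table cell. The 7-day rule already requires injection dates. Two small additions are needed: the reason for stopping, which Table 1 does not list, and a statement of how the Week 25 injection is scored, since its window runs one week past the last visit. The downside is that reported adherence may be lower, by up to about 20 points if many stop early.
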